#### **14.4.2 Vigilance reporting according to Article 80 of the MDR**

The following events are considered reportable events in accordance with MDR Art. 80(2):

- any serious adverse event that has a causal relationship with the investigation procedure or where such causal relationship is reasonably possible.

For the purpose of harmonizing reports, each SAE will be classified according to four different levels of causality as per definitions of the MDCG 2020-10/1 specified in the safety management plan:

1. Not related
2. Possible
3. Probable
4. Causal relationship

Only causality level 1 (i.e. "not related") is excluded from reporting.

**Strictly Confidential**

Any serious adverse event that has a causal relationship with an investigational procedure will be reported by the investigator to the sponsor ([[contact]](mailto:[contact])) and/or [contact] (as back-up method) and to the Vigilance manager [name] ([[contact]](mailto:[contact])), to the CRO ([[contact]](mailto:[contact])) and/or [contact]), to the EU representative [name] ([[contact]](mailto:[contact])), and to the local CRA ([[contact]](mailto:[contact])) **immediately, but not later than 3 calendar days** after investigation site study personnel's awareness of the event. To this end, the investigator will complete the "SAE form" (appendix C).

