### 5.5.2 Placebo

Isotonic saline nasal solutions are well known for cleansing and hydrating the nasal mucosa without any safety concern. No risk analysis has been conducted to estimate the risk associated with each step of this device lifecycle. Anyway, the residual risk for the Placebo is expected to be lower than for Healsea Rescue\* since this latter contains Symbiofilm® and hypertonic saline solution and therefore represents the worst case. Thus, the Placebo used during this study can also be considered as safe.

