## **14. Vigilance**

### **14.1 General**

Healsea® Rescue\* will be used in the intended use covered by the CE mark in this PMCF study.

Pursuant to (EU)2017/745 Medical Device Regulation, for a post market clinical follow-up investigation of a medical device used within the intended use covered by the CE-mark, requirement of MDR articles 87 to 90 apply (materiovigilance).

Nevertheless, if a causal relationship between a serious adverse event and an investigational procedure has been established, the safety reporting laid down in Article 80 of the MDR. Since the electronic system referred to in Article 73 (Eudamed) will not be available and fully functional at the date of study start, the procedures for safety reporting will be performed according to modalities described in the MDCG 2020-10/1 and -10/2.

All modalities of safety reporting will be detailed in a Safety Management Plan signed by the sponsor vigilant, the Principal Investigators, the local CRA in charge of the monitoring and a representant of the CRO.

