### **14.2 Definitions**

**Incident** means any malfunction or deterioration in the characteristics or performance of a device made available on the market, including use-error due to ergonomic features, as well as any inadequacy in the information supplied by the manufacturer and any undesirable side-effect (MDR 2017/745).

**Serious incident** means any incident that directly or indirectly led, might have led or might lead to any of the following: (a) the death of a patient, user or other person, (b) the temporary or permanent

serious deterioration of a patient's, user's or other person's state of health, (c) a serious public health threat (MDR 2017/745).

**Serious public health threat** means an event which could result in imminent risk of death, serious deterioration in a person's state of health, or serious illness, that may require prompt remedial action, and that may cause significant morbidity or mortality in humans, or that is unusual or unexpected for the given place and time (MDR 2017/745).

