**Appendix C: SAE form**

This form is to be used when a causal relationship between the serious adverse event and the additional investigational procedure is suspected (art 80.5 and 80.6).

This form is to be completed immediately and no later than 3 days after the investigation site personnel have been made aware of the event and sent immediately to the Clinical Study Monitor by mail [contact] and to BG Clinicals [[contact]](mailto:[contact]), FAX: no [contact], to the sponsor [[contact]](mailto:[contact]) and/or [contact] (as back-up method) and to the Vigilance Manager [name] ([[contact]](mailto:[contact])) and the EU representative ([[contact]](mailto:[contact])).

Protocol title: Efficacy and safety of Healsea® hypertonic nasal spray 2.7 % in the treatment of acute infectious rhinitis in adults	Acronym: TEACHER			
Sponsor code: LPH-2201	Competent Authority(ies) reference number:			
Transmission date: 

 	 	 	

 ddmmyy				

SAE# (to be completed by the sponsor)	First notification: 	Follow-up: 	Final: 
--	--	-------------------------------------	---------------------------------

1. Subject information													
Birthdate: 

 	 	 	 	 	 	

 mm/yyyy							Gender: Male  Female  Other 						
Height: 

 	 	 	 	

 cm					Weight: 

 	 	 	 	

 , 

 	 	

 Kg								
Investigational arm:	 Healsea® Rescue	 Placebo	 blinded										

2. Description of the SAE	
The serious adverse event resulted in:	 Medical or surgical intervention to prevent life threatening illness or injury or permanent impairment to a body structure or a body function  Chronic disease  Foetal distress, foetal death or congenital physical or mental impairment or birth defect

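### Section 14.4.2 ties the investigator's 3-day SAE deadline to a narrower causality trigger than the rest of the protocol uses, and the incident definition does not clearly cover the placebo spray

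*Protocol*

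**What the plan says.** Protocol section 14 sets up two prompt reporting routes from the investigator to the sponsor.

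**Study procedures (Article 80 route).** Section 14.4.2 defines as reportable "any serious adverse event that has a causal relationship with the investigation procedure or where such causal relationship is reasonably possible". It lists four causality levels (not related, possible, probable, causal relationship) and says that only the first "is excluded from reporting". The sentence that then tells the investigator what to do is "Any serious adverse event that has a causal relationship with an investigational procedure will be reported by the investigator to the sponsor", followed by the other recipients, the limit "immediately, but not later than 3 calendar days" from site awareness, and the form to use. Section 14.1 introduces this route with the condition "if a causal relationship between a serious adverse event and an investigational procedure has been established". The header of Appendix C says "This form is to be used when a causal relationship between the serious adverse event and the additional investigational procedure is suspected".

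**Device (materiovigilance route).** Section 14.4.1 sends all incidents and expected side effects to the sponsor, in under 24 hours if serious and under 48 hours if not. Section 14.2 defines an incident by reference to "any malfunction or deterioration in the characteristics or performance of a device made available on the market", and also includes undesirable side-effects. Section 14.1 bases this route on use within the CE-marked purpose.

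For the placebo, section 5.5.2 states "No risk analysis has been conducted to estimate the risk associated with each step of this device lifecycle". It adds that residual risk should be lower than for the active spray, which it treats as the worst case.

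**The concern.** An SAE trigger has to be read the same way by whoever applies it. Here the sentence that carries the duty uses the label of the highest causality level, and section 14.1 asks for an established relationship. Elsewhere a reasonable possibility or a suspicion is enough. An investigator who follows the narrow wording would not send an event rated possible or probable. The sponsor would then depend on the e-diary and eCRF, for which section 14.3 gives validation at V2 but no SAE deadline.

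Two other parts of the protocol depend on a clear trigger. Section 5.5.3 tracks reporting timelines and unreported events against thresholds. Section 15 has the sponsor suspend the study on suspicion of unacceptable risk.

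The second question is whether a serious event suspected to come from the placebo spray is an incident at all. The definition is written for marketed devices, and CE marking is stated only for Healsea Rescue (sections 3.1.1, 3.2 and 14.1).

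**Working it through.** No statistical calculation applies. The check sets the wordings side by side and counts the causality levels that each covers when read literally.

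**Procedure route**

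| Place | Trigger, in short | Levels covered (of 4) | Time limit given there |
|---|---|---|---|
| 14.1 | relationship established | level 4 | none |
| 14.4.2, definition and list of levels | causal or reasonably possible; only level 1 excluded | levels 2, 3, 4 | none |
| 14.4.2, operative sentence | has a causal relationship | level 4 | 3 calendar days from site awareness |
| 14.5.2, sponsor's duty | causal or reasonably possible | levels 2, 3, 4 | 2 or 7 calendar days from sponsor awareness |
| Appendix C, header | suspected | levels 2, 3, 4 | 3 days from site awareness |

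Reportable by definition: 4 − 1 = 3 levels. Covered by the operative sentence: 1 level. Difference: 3 − 1 = 2 levels, possible and probable.

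The operative sentence and Appendix C concern the same form and the same 3-day limit, but give it different triggers. The sponsor's 2- and 7-day limits both run from sponsor awareness. An event held back under the narrow wording therefore starts neither.

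**Device route and the placebo**

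1. Against coverage: the incident definition refers to a marketed device (14.2); the legal basis given is CE-marked use (14.1); the documents do not describe the placebo as CE marked or marketed.
2. For coverage: 14.4.1 has no restriction by arm; Appendix B sets 24 hours for any serious safety issue; the investigator, CRO and sponsor are blinded (7.1.2); SAP section 11.2 treats as an incident any adverse event whose relationship to study device is other than not related; the SAP's incident table shells have a Placebo column.
3. Forms: section 5 of Appendix C asks for causality with the study procedure only, and Appendix B has no causality field. Yet the SAP definition of an incident rests on relationship to the device, and its incident listing has a causality column.

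The two issues are independent. Widening the operative sentence of 14.4.2 to levels 2 to 4 would still leave it limited to procedures, so it would not settle the status of the placebo spray.

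**The case against.** The strongest reply on the procedure route is that the operative sentence should not be read alone. It follows directly after the statement that only unrelated events are excluded, in a section headed as the investigator's responsibilities. The form it requires is triggered by suspicion, carries the same 3-day limit and has boxes for possible and probable. A careful investigator would probably report all three levels. That stands, and it limits the practical effect: the two-level gap exists only on a literal reading of one sentence. It does not remove the contradiction between 14.1 and that sentence on one side and the definition, 14.5.2 and Appendix C on the other. Procedure-related SAEs should also be rare, since section 5.3 names only questionnaires and two swabs.

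Four stronger readings are tempting, and the documents do not support them:

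- *Serious events from the placebo spray have no prompt route.* Section 14.4.1 and Appendix B are not restricted by arm. The protocol calls both sprays medical devices (7.1.2).
- *Serious events would be handled differently by arm.* A blinded investigator cannot filter by arm. The definitional gap could matter only after an unblinding or at the sponsor's onward step.
- *An affected event would reach the sponsor 12 to 14 days late (D1 to V2 at D13 to D15).* This is an unqualified worst case. The 3-day limit runs from site awareness, patients record adverse events daily, and e-diary entries upload automatically to the eCRF (9.2). None of this is an SAE duty with a deadline, but it makes the figure unsafe to quote.
- *The protocol is wrong not to require prompt reporting of every SAE.* Section 14.4.2 excludes unrelated events explicitly. Changing that is a sponsor policy choice.

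Finally, section 14.1 leaves the detailed reporting arrangements to a safety management plan that is not among the documents. It may resolve both points in practice, but it would not correct the protocol text.

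**Conclusion.** The contradiction in the procedure trigger is real. The definition, the sponsor's duty and the SAE form cover three of four causality levels; the operative sentence in 14.4.2 and section 14.1, read literally, cover one. On that reading 14.4.2 gives the investigator no deadline for possible or probable events, and only the header of Appendix C supplies one.

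The placebo point is smaller. It is an unclear definition, not a missing route, and the rest of the protocol and the SAP indicate that incidents are meant to be reported in both arms.

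Both conclusions rest on the protocol and SAP text alone. The documents give no expected SAE rate, so the number of events affected cannot be estimated. The change is worth making because it concerns a safety trigger and costs almost nothing.

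**What to change.** 1. Reconcile section 14.1 and the operative sentence of 14.4.2 with the reportable definition, 14.5.2 and Appendix C. The operative sentence should name levels 2 to 4 (possible, probable, causal relationship) and keep its 3-day limit.
2. State in 14.4.1 that the investigator's incident reporting applies to the blinded spray in either arm. Use the working definition in SAP section 11.2: relationship to study device other than not related.
3. Add a causality line for the blinded spray to the reporting forms (Appendices B and C).
4. Check that the safety management plan uses the same triggers.

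The cost is protocol and form wording, with at most a few extra forms during the study. No analysis changes. The sponsor's onward obligations for the placebo depend on its regulatory status, which the documents do not give, so this fix is limited to the investigator's step.

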## 14.5 Sponsor responsibilities and processing timelines

### 14.5.1 Materiovigilance

The vigilance manager of Lallemand Pharma is responsible for the reporting to the Bulgarian Competent Authority.

Briefly, for serious incidents or risk of serious incident, the vigilance manager will complete a Manufacturer Incident Report. The result of the investigation conducted by the sponsor may lead to the implementation of a safety corrective action and completion of a Field Safety Corrective Action (FSCA) and of a Field Safety Notice. These documents will be transmitted to the Bulgarian Competent Authority in accordance with the timelines provided in the table below:

Serious Public Health Threat	Report immediately but not more than 2 days
Death or UNANTICIPATED Serious Deterioration in status of health	Report immediately but not more than 10 days
Others (could have led to death or serious deterioration in health)	Report immediately but not more than 15 days
Every FSCA	Immediately before the measure is implemented except in case of emergency, when the vigilance manager of the sponsor has to immediately take a safety corrective action

Increase rate or severity of expected undesirable side effects and non-serious incidents will be reported to the Bulgarian Competent Authority in Trend reports as per regulation requirements.

Responsibilities of sponsor are detailed in the Safety Management Plan.

### 14.5.2 Vigilance according to Article 80

Any serious adverse event that has a causal relationship with an additional procedure or a causal relationship reasonably possible, will be reported by the sponsor to the Bulgarian CA and the Ethics Committee if applicable as follows:

Any serious adverse event that has a causal relationship with the additional procedure or a causal relationship reasonably possible, will be reported to the Bulgarian CA by the sponsor as follows: Imminent risk of death, serious injury, or serious illness and that requires prompt remedial action for patients/subjects or a new finding to it	Immediately, but not later than 2 calendar days after awareness by sponsor of a new reportable event or of new information in relation with an already reported event. The excel file provided by the MDCG 2020-10/2 is to be used.
Other reportable events or a new finding/update to it	Immediately, but not later than 7 calendar days following the date of awareness by the sponsor of the new reportable event or of new information in relation with an already reported event. The excel file provided by the MDCG 2020-10/2 is to be used.

## **15. Suspension, or premature termination of the Clinical Investigation**

Lallemand Pharma AG may suspend or prematurely terminate the clinical investigation. The reasons shall be documented. Reasons for suspension or premature termination at an investigation site may include occurrences where monitoring or auditing identifies serious or repeated deviations on the part of an investigator. Lallemand Pharma AG will notify the Regulatory Authority as appropriate and ensure that the EC is notified of any suspension or early termination of the clinical investigation.

If suspicion of an unacceptable risk to subjects arises during the clinical investigation, or when so instructed by the EC or Regulatory Authority, Lallemand Pharma AG will suspend the clinical investigation while the risk is assessed. The sponsor will terminate the clinical investigation if an unacceptable risk is confirmed. The decision to maintain or to unblind the study will be taken in consultation with the Regulatory Authority. Should the risk not be confirmed Lallemand Pharma AG will, in accordance with regulations, provide relevant persons with justification and data supporting the decision to resume the clinical investigation.

EC or Regulatory Authority may suspend or prematurely terminate participation of one site or of all the participating sites.

The patients will receive all treatments needed in case of complication or safety issues. In this case, the patient will be followed until the end of the issue.

## **16. Publication policy**

The information and data collected during the conduct of this clinical study are considered confidential and are used by the sponsor in connection with the development of the study treatment. This information will be disclosed by the sponsor depending on current regulations.

***Strictly Confidential***

To allow use of the information derived from this clinical study and to ensure compliance with current regulations, the investigator must provide the sponsor with complete test results and all data collected during the study.

Only the sponsor may make study information available to physicians and to Regulatory Agencies, except as required by current regulations.

All the results of this study including data and reports are the property of the sponsor.

In the event that the sponsor chooses to publish study data, the manuscript must be provided to the author(s) at least 30 days prior to the expected date of submission to the intended publisher.

The investigator(s) can reserve the right to publish or present study data; if so, the manuscript or abstract must be provided to the sponsor for review at least 30 days prior to the expected date of submission to the intended publisher or of planned presentation.

In addition, if necessary, (the) investigator(s) shall withhold publication for an additional 60 days, to allow the filing of a patent application, or to allow the sponsor to take any measures he deems appropriate to establish and preserve his proprietary rights.

It is agreed that publication of study results by each site shall be made only as part of a publication of the study results obtained by all sites performing the protocol, once the study is completed and finalised.

A description of the clinical investigation is registered in <https://www.clinicaltrials.gov/>. The content will be updated throughout the conduct of the clinical investigation and the results entered at completion of the clinical investigation and made publicly available.

## **List of Appendix**

Appendix A: Instructions for Use (IFU)

Appendix B: Primary Notification Form (PNF)

Appendix C: Serious Adverse Event (SAE) form

Appendix A: IFU

## HEALSEA® RESCUE

INDICATION Healsea® RESCUE is a nasal spray indicated in adults over 18 years in the treatment of nasal symptoms of acute rhinitis and rhinosinusitis, reduces swelling of the nasal mucosa.	UNDESIRABLE EFFECTS Feeling of itching and irritation can occur while initiating the treatment. In case of undesirable effects, contact your doctor.
COMPOSITION Hypertonic saline solution (salinity 2.7%), Symbiofilm®.	STORAGE AND WASTE RECOMMENDATION Store at room temperature and not above 30°C. See the expiry date on the box or the bottle. Ask your pharmacist to throw out the bottle after use. These measures contribute to protect the environment.
DIRECTION OF USE One-two sprays twice a day in each nostril for 7 days or as recommended by your doctor or pharmacist.	TECHNOLOGY The spray pump APF (Advanced Preservative Free) uses a technology that permits to dispense a preservative free solution.
PRECAUTION OF USE - Keep out of reach of children. - If symptoms persist more than 7 days, ask for advices to your doctor or pharmacist. - The bottle shall be used by only one person for hygiene reason and to avoid the transmission of pathogenic agents that could be in contact with the nozzle.	HOW TO USE HEALSEA® RESCUE? 1. Place the nozzle smoothly into the nostril while keeping head straight. 2. Once the nozzle is placed, press on the nozzle in each nostril. Let flow the excess of solution and wipe. 3. Clean the nozzle with tissue, soapy water, rinse and dry after every use.
CONTRAINICATION Do not use in children and adolescents under 18 years. Do not use in case of hypersensitivity or allergy to one or several components.	

**Healsea® RESCUE** is a nasal spray containing hypertonic saline solution mixed with an innovative extract, Symbiofilm®, isolated from the marine biosphere.

**Healsea® RESCUE** is a natural care preservative free allowing to treat nasal symptoms of acute rhinitis and rhinosinusitis.

Symbiofilm® is a marine postbiotic, which contains exopolymeric substances, that enhances mechanically the cleansing efficiency of hypertonic water.

Symbiofilm® reduces the development of biofilm from respiratory pathogenic microorganisms by mechanical action as well as the mucosal adhesion and helps reducing the spreading of viruses *in-vitro*.

**Healsea® RESCUE** is the ideal solution to ensure an efficient cleansing, moisturizing and decongestion of the nasal mucosa by osmotic action.

Lallemand Pharma AG  
[name]  
[name]  
Switzerland

Learn more about  
biofilms by flashing  
this QR code!

Publication date:  
2021/12/10\_R1

EC REP

ASPE CONSEIL  
[name]  
[name]

LALLEMAND  
LALLEMAND PHARMA

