**Strictly Confidential**

	
 
with Healsea® Rescue*, 2 puffs in each nostril 2 times per day during 7 days (14 intakes of the investigational device).
 
 
or
 
 
with isotonic nasal spray (Placebo), 2 puffs in each nostril 2 times per day during 7 days (14 intakes of the Placebo).
 
 
- Part 2 (D9-D13/15): follow-up phase.
 
Visit 1 (V1) - (Day 1): Screening/Inclusion/Randomization Information and consent, demographic data and medical history, ongoing medication, physical and clinical examination (including COVID-19 antigen test), inclusion/non-inclusion criteria, randomization, e-diary presentation (including the first study questionnaire completion), reporting of adverse events, dispensation of Healsea® Rescue* Nasal Spray or Placebo (Isotonic nasal spray) (according to randomization list).
 
D1-D8 (at home): Daily completion of the electronic diary (questionnaire, adverse events/incidents and concomitant medications), Healsea® Rescue* /Placebo nasal spray treatment daily administration.
 
D8 (Telephone call): End of Healsea® Rescue*/Placebo nasal spray treatment.
 
D9-D13/15 (at home): Daily completion of the electronic diary (adverse events/incidents, concomitant medications, WURSS-21 if applicable, until the subject feels not sick for two consecutive days).
 
Visit 2 (V2) – (Day 13-15): end of study Physical and clinical examination (including COVID-19 antigen test), diary review, reporting of adverse events and incidents, compliance, subject satisfaction, WURSS-21 completion if the patient has not ticked “not sick” for 2 consecutive days in the previous days.

Number of Subjects:	A sample of 180 subjects (90 subjects per group) will be needed to provide 80% power with a 1-sided test at a 0.05 significance level to detect a difference between Healsea® Rescue* and Placebo groups AUC of 30%. Assuming that approximately 10% of subjects may drop-out the study, 200 will be randomly assigned at a ratio 1:1 to Healsea® Rescue* and Placebo (100 subjects per group).
Target Population:	Adults with acute infectious rhinitis

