### 3. Identification and description of the investigational device and of the Placebo

#### 3.1 Summary description

##### 3.1.1 The investigational device

**Healsea® Rescue\*** is a CE marked nasal spray composed with a hypertonic saline solution (2.7% NaCl) and Symbiofilm® (0.04%) (Table 1). Symbiofilm® is a Lallemand proprietary marine postbiotic composition including an exopolysaccharide mainly composed of N-acetyl hexosamines, acidic and neutral monosaccharides.

*Table 1 : Qualitative and quantitative composition of Healsea Rescue\**

Ingredient	Concentration (g/L)
NaCl	27 g/L
Symbiofilm®	0.4 g/L
Purified Water	QS 1L

Healsea® Rescue\* is a class I medical device (in accordance with the rule 5 of the annex IX of European Council Directive 93/42/EEC).

In accordance with annex IX of European Council Directive 93/42/EEC, the medical device classification is based on the following characteristics:

- Duration of continuous use: Short-term (60 min to 30 days)
- Type of device: Invasive, with respect to body orifice, non-active, not surgically inserted, no implantable device
- Location of action: Nasal cavity

The primary packaging is a plastic bottle with atmospheric pump in 20 ml format.

Healsea® Rescue\* is indicated in adults over 18 years in the treatment of symptoms of acute respiratory tract infections: rhinitis or rhinosinusitis, reduces swelling of the nasal mucosa.

One-two sprays, twice a day in each nostril during 7 days or as recommended by the doctor or pharmacist.

The technical performances are summarised below:

*Table 2 : Technical performances of Healsea Rescue\**

Component	Function(s)
Hypertonic saline solution 2.7 %	
 
- Improve nasal mucosa function
 
- Clean the nasal cavity and eliminate allergens and infectious agents
 

Symbiofilm®	
 
- Enhancing the cleansing efficacy
 
- Reducing biofilm formation
 

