### 3.7.3 Primary and secondary packaging and labelling

The primary packaging is a white vial (Figure 2)

*Figure 2 : primary packaging*

The secondary packaging is a white cardboard box.

A white label is sticked on the primary packaging with the following mentions:

LPH-2201 / TEACHER

Saline hypertonic solution 2.7% and Symbiofilm 0.04% (Healsea® Rescue) or isotonic nasal saline solution (Placebo).  
Nasal spray, nasal route, vial 20 ml  
Posology: two sprays, twice a day in each nostril during 7 days

Patient: \_\_\_\_\_

Investigator: \_\_\_\_\_

Batch number: \_\_\_\_\_

Site: DCC Convex EOOD  
[name]  
[name]

Treatment: \_\_\_\_\_

Expiry Date (mm/yyyy): \_\_ / \_\_ \_\_

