**For Clinical Investigation use only**

A white label is sticked on the secondary packaging with the following mentions:

LPH-2201 / TEACHER

Saline hypertonic solution 2.7% and Symbiofilm 0.04% (Healsea® Rescue)  
or isotonic nasal saline solution (Placebo).  
Nasal spray, nasal route, vial 20 ml  
Posology: two sprays, twice a day in each nostril during 7 days

Patient: \_\_\_\_\_

Investigator: \_\_\_\_\_

Batch number: \_\_\_\_\_

Site: DCC Convex EOOD  
[name]  
[name]

Treatment: \_\_\_\_\_

Expiry Date (mm/yyyy): \_\_ / \_\_ \_\_

Please refer to the leaflet - Store at room temperature up to 30°C - Keep out of the reach of children

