### **3.9 Reference to the IFU**

A IFU leaflet is included in each secondary packaging: on one face, the IFU of Healsea® Rescue\*, on the other face, the IFU of Healsea® Placebo (See appendix 1).

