### 7.2 Investigational device and comparator

#### 7.2.1 Description of the exposure to the investigational device

The investigational device will be **Healsea® Rescue\***. This is a CE marked Medical Device used for acute infectious rhinitis and administered by spraying 2 puffs in each nostril 2 times per day during 7 days (14 intakes of the investigational device).

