## 7.2.2 Description and justification of the choice of the comparator

Clinical batches are manufactured by C.O.C Farmaceutici and the blinding of the investigational devices is ensured by Creapharm, [name], Email: [contact].

The comparator is an isotonic saline nasal spray indistinguishable from the **Healsea® Rescue\*** product. Posology, instructions for use, contraindications, precaution of use and labelling are identical to those for **Healsea® Rescue\***.

We hypothesize that hypertonic saline solution and Symbiofilm™ will act in a synergistic manner for achieving the principal action, i.e. reduction of the duration of acute rhinitis symptoms. Placebo is classically defined as a pharmaceutically inert substance. This definition can of course be extended to the present study evaluating the Medical Device **Healsea® Rescue\***. Thus, we have chosen isotonic saline solution which can be considered as inert Placebo i.e. neutral for the nasal mucosa. Nevertheless, nasal irrigation with isotonic saline solution is known to have some efficacy in reducing common cold symptomatology.

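### Both faces of the study leaflet allow one or two sprays per nostril, while the labels and protocol fix two; one spray at every intake would read about 50% to 53% compliance, below the 80% limit

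*Protocol*

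**What the plan says.** The documents give the patient's dose in two forms.

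- **Leaflet (Protocol Appendix A).** The Healsea Rescue face and the Placebo face carry the same direction of use: "One-two sprays twice a day in each nostril for 7 days or as recommended by your doctor or pharmacist". Section 3.9 confirms that every patient gets it: "A IFU leaflet is included in each secondary packaging". The range is the marketed posology, which section 3.1.1 gives as "One-two sprays, twice a day in each nostril during 7 days or as recommended by the doctor or pharmacist".
- **Labels (Protocol section 3.7.3).** Bottle and box both read "Posology: two sprays, twice a day in each nostril during 7 days". The box label adds "Please refer to the leaflet".
- **Study dose (Protocol section 7.2.1).** The device is "administered by spraying 2 puffs in each nostril 2 times per day during 7 days", in 14 intakes. The Synopsis says the same for both arms.

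Section 7.2.2 states of the comparator: "Posology, instructions for use, contraindications, precaution of use and labelling are identical to those for" the test product.

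Compliance is measured by weighing the returned bottle at V2 (Protocol section 7.4.1; formula in SAP section 9). A result under 80% or over 120% is a major deviation (Protocol section 11, SAP section 7.2). Major deviators are left out of the per-protocol (PP) set (SAP section 5), after validation at the data review meeting.

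**The concern.** The patient holds two written instructions that differ at the lower end, and the box label directs the patient from the fixed dose to the looser one. Nothing study-specific was added to the leaflet, although the packs were prepared specially for this trial (section 3.8) and a placebo face was written for it. The how-to-use steps on each face mention pressing the nozzle in each nostril and say nothing of a second press, so one spray is a natural reading.

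A patient who follows the leaflet at its lower end receives half the tested dose, stays in the full analysis set (FAS) under-dosed, and may be classed as a major deviator for doing what the leaflet permits. No step described during treatment would catch it. The e-diary items listed are WURSS-21, adverse events and concomitant medication, with no spray count. The D8 call is a reminder to stop. Weighing takes place at D13 to D15, when correction is no longer possible.

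**Working it through.** **Inputs**

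- Initial bottle weight 33 g; theoretical end weight 27.7 g (SAP section 9).
- Dose: 2 puffs × 2 nostrils × 14 intakes = 56 actuations (Protocol section 7.2.1).
- Volume per activation: 100 ± 20 µL (Protocol section 3.7.1).
- Density: not given. Assumed 1.0 g/mL; a value of 1.018 g/mL is tried below.
- Priming: the investigator primes the pump at V1 (Protocol section 7.4.1), but the number of puffs is not stated. Results are before priming loss.

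**The plan's own figure.** The denominator is 33 − 27.7 = 5.3 g, which the SAP uses. It implies 5.3 / 56 = 0.0946 g per actuation. The nominal full course is 56 × 0.10 = 5.60 g, or 105.7%, and the tolerance limits give 4.48 g to 6.72 g. So 5.3 g does represent the two-spray course.

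**One spray at every intake.** 1 × 2 nostrils × 14 = 28 actuations. Compliance (%) = weight loss × 100 / 5.3.

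| Mass per actuation | One spray throughout | Two sprays throughout |
|---|---|---|
| 0.08 g (lower limit) | 2.24 g, 42.3% | 4.48 g, 84.5% |
| 0.0946 g (SAP calibration) | 2.65 g, 50.0% | 5.30 g, 100.0% |
| 0.10 g (nominal) | 2.80 g, 52.8% | 5.60 g, 105.7% |
| 0.12 g (upper limit) | 3.36 g, 63.4% | 6.72 g, 126.8% |

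At 1.018 g/mL the nominal one-spray figure becomes 53.8%. Every one-spray result is under 80%.

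**One spray at only some intakes.** With one spray at k of 14 intakes, 56 − 2k actuations remain. The smallest k that reads under 80% is:

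- SAP calibration: k = 6 (44 actuations, 78.6%; k = 5 gives 82.1%)
- nominal: k = 7 (42, 79.2%; k = 6 gives 83.0%)
- lower limit: k = 2 (52, 78.5%; k = 1 gives 81.5%)
- upper limit: k = 11 (34, 77.0%; k = 10 gives 81.5%)

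**Could priming hide it?** Reaching 80% needs 0.8 × 5.3 = 4.24 g. An all-one-spray patient would need 15 priming puffs at nominal ((28 + 15) × 0.10 = 4.30 g, 81.1%), 8 at the upper limit (36 × 0.12 = 4.32 g, 81.5%) or 25 at the lower limit (53 × 0.08 = 4.24 g, 80.0%).

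**The case against.** The strongest reply is that the conflict is partial and mostly resolved already. Two sprays satisfies every text. The leaflet defers to the doctor's recommendation, both labels state two, and the investigator instructs each patient (Protocol sections 3.8 and 7.4.1). A one-spray patient would have to set all that aside. Excluding under-dosed patients from a supportive set is what the 80% rule is for. SAP Table 14.1.3 and Listing 16.2.5.2 would show widespread under-dosing.

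Much of this stands. The risk is small, its frequency cannot be estimated from the documents, and the reporting would reveal it. The tolerance limits are also bounding cases, since they put every actuation of a course at the limit. The early crossing at 2 of 14 intakes arises mainly because a fully compliant patient already reads 84.5% there, which is a matter of pump calibration and not of the leaflet.

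What does not follow is that the leaflet can be left alone. The safeguards make one-spray use less likely but leave the contradiction in the document the box label cites, and the tables show it only after treatment. Timing is a fair point: SAP section 12 describes patients' questionnaire answers in the past tense, so some packs had been used when it was written. The correction helps only packs not yet dispensed.

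**Conclusion.** The concern holds. A patient-facing instruction in the plan permits half the study dose, and following it at every intake gives about 50% to 53% measured compliance (42.3% to 63.4% across the pump tolerance), short of 80% in every case. This rests on 1.0 g/mL and on no priming loss, though neither assumption plausibly changes the conclusion.

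The consequence is limited. The primary FAS analysis loses no one, but keeps any such patient at half dose. Exclusion touches only the supportive PP analyses and depends on the data review meeting. With identical wording on both faces and the same posology in both arms, no imbalance between arms is built in. The patient information sheet was not among the documents reviewed, so what it says on dose cannot be judged. This is an inexpensive correction that should be made, and it does not put the primary result in doubt.

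**What to change.** Before dispensing, change or overlabel the direction of use on both leaflet faces to: *For this study: two sprays in each nostril, twice a day, for 7 days (14 intakes)*. No change to the compliance formula is proposed here.

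The cost is a small reprint or overlabel, plus a dated amendment signed by the sponsor and the Principal Investigator, because the leaflet is an appendix to the protocol (Protocol section 10). If the sponsor judges the amendment substantial, the ethics committee and competent authority must also be notified. The marketed leaflet, the data and the analysis are unaffected.
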